5.3 Flowchart of the study cohort assembly

For rivaroxaban vs. warfarin

	Optum		Truven		Medicare	
	Less Excluded Patients	Remaining Patients	Less Excluded Patients	Remaining Patients	Less Excluded Patients	Remaining Patients
All patients		75,894,642		200,203,908		6,886,908
Did not meet cohort entry criteria	-74,960,282	934,360	-199,073,812	1,130,096	-2,028,461	4,858,447
Excluded due to insufficient enrollment	-92,301	842,059	-95,091	1,035,005	-1,551,114	3,307,333

Excluded due to prior use of referent	-482,398	359,661	-622,538	412,467	-2,080,069	1,227,264
Excluded due to prior use of exposure	-205,565	154,096	-204,425	208,042	-660,796	566,468
Excluded because patient qualified in >1 exposure category	-7	154,089	-26	208,016	-81	566,387
Excluded based on Age	-624	153,465	0	208,016	-155	566,232
Excluded based on Gender	0	153,465	0	208,016	0	566,232
Excluded based on Inclusion #1 - Age >=18	-86	153,379	-264	207,752	-65	566,167
Excluded based on Inclusion #2 & 3 - Atrial fibrillation	-83,438	69,941	-129,172	78,580	-348,521	217,646
Excluded based on Inclusion #4	-13,297	56,644	-16,046	62,534	-36,136	181,510
Excluded based on Exclusion #1a - Mitral stenosis	-275	56,369	-154	62,380	-399	181,111
Excluded based on Exclusion #1b - Prosthetic heart valve	-1,238	55,131	-789	61,591	-3,016	178,095
Excluded based on Exclusion #1e - atrial myxoma or left ventricular thrombus	-158	54,973	-35	61,556	-234	177,861
Excluded based on Exclusion #1f - Active infective endocarditis	-279	54,694	-138	61,418	-401	177,460
Excluded based on Exclusion #2a - Active bleeding or bleeding history	-3,413	51,281	-2,716	58,702	-8,256	169,204
Excluded based on Exclusion #2b.1 - Major Surgery	-1,564	49,717	-1,561	57,141	-6,484	162,720
Excluded based on Exclusion #2b.2 - Bleeding diathesis	-1,235	48,482	-885	56,256	-3,832	158,888
Excluded based on Exclusion #2b.3 - Intracranial neoplasm, AV malformation, cerebral aneurysm	-259	48,223	-283	55,973	-422	158,466
Excluded based on Exclusion #2d - Thrombocytopenia	0	48,223	0	55,973	0	158,466
Excluded based on Exclusion #2e - Uncontrolled hypertension	-47	48,176	-105	55,868	-300	158,166
Excluded based on Exclusion #3a.1 - stroke plus disabling stroke effects	-257	47,919	-152	55,716	-847	157,319
Excluded based on Exclusion # 3a.2 - stroke	-103	47,816	-88	55,628	-642	156,677
Excluded based on Exclusion #3b - TIA	-17	47,799	-25	55,603	-123	156,554
Excluded based on Exclusion #3c - DVT & PE	-1,095	46,704	-853	54,750	-3,185	153,369

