Excluded based on Exclusion #3d.1 - Use of aspirin > 100 mg, #3d.2 - Use of fibrinolytic agents, #3d.3 - Use of Aspirin + thienopyridines, #3d.4 - Use of cangrelor, #3f - Use of CYP inhibitors, #3g - Use of CYP inducers	-1,020	45,684	-1,024	53,726	-4,503	148,866
Excluded based on Exclusion #3h – Anemia & #3i - Pregnancy	-1,382	44,302	-1,294	52,432	-6,940	141,926
Excluded based on Exclusion #3k - HIV infection	-13	44,289	-7	52,425	-12	141,914

Excluded based on Exclusion #3l - Severe renal impairment	-3,281	41,008	-2,012	50,413	-7,391	134,523
Excluded based on Exclusion #3m - Liver disease	-192	40,816	-170	50,243	-466	134,057
Excluded based on Exclusion #4a - CCI (180 days)- ICD9 and ICD10 v2	-40	40,776	-31	50,212	-400	133,657
Excluded based on Exclusion #4b - drug addiction or alcohol abuse	-157	40,619	-106	50,106	-231	133,426
Excluded based on Exclusion #4f - Non-compliance	-15	40,604	-21	50,085	-196	133,230
Final cohort		40,604		50,085		133,230

Due to CMS cell suppression policy, all values less than 11 are denoted with **

* Medicare database includes all patients using a novel oral anticoagulant and a subset of patients using warfarin during 2011-2017.

6. Variables

6.1 Exposure-related variables:

Study drug:

The study exposure of interest is initiation of rivaroxaban. Initiation will be defined by no use of rivaroxaban or a comparator in the prior 6 months before treatment initiation (washout period).

Comparator agents-

- Initiators of rivaroxaban will be compared to initiators of-
 - Warfarin

6.2 Covariates:

- Age
- Sex
- Combined Comorbidity Index (CCI), measured over the baseline covariate assessment period, defined as 180 days prior to and including index date

Covariates listed above represent only a small subset of covariates that will ultimately be controlled for in the design and analysis. We use the covariates above only for initial feasibility analyses to judge whether there is likely to be sufficient overlap between treatment groups to proceed with the study. Remaining covariates are defined only after the study has passed the initial feasibility analysis and the initial power assessment and are listed in Table 1 (**Appendix B**).

6.3 Outcome variables and study follow-up:

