After review of initial feasibility and power analyses, complete creation of the remaining covariates (see Table 1 below for list of covariates). Again, using the dummy outcome of a 90-day gap in database enrollment, complete a 1:1 PS-matched analysis. The PS should include the complete list of covariates (excluding laboratory values, which are missing in some patients).

- Provide plot of PS distributions stratified by treatment group.

Note- Please refer to **Appendix B**.

- Report covariate balance after matching.

Note- For Table 1, please refer to **Appendix B**.

- Report reasons for censoring by treatment group.

	Overall	Referent	Exposure
Dummy Outcome	0 (0.00%)	0 (0.00%)	0 (0.00%)
Death	1,879 (1.83%)	946 (1.84%)	933 (1.82%)
Start of an additional exposure	3,238 (3.15%)	1,642 (3.20%)	1,596 (3.11%)
End of index exposure	71,983 (70.13%)	36,022 (70.19%)	35,961 (70.07%)
Specified date reached (Dec 17/Dec 18/Dec 19)	6,822 (6.65%)	3,196 (6.23%)	3,626 (7.07%)
End of patient enrollment	5,237 (5.10%)	2,408 (4.69%)	2,829 (5.51%)
Switch to other NOACs (for censoring) + nursing home admission	13,477 (13.13%)	7,104 (13.84%)	6,373 (12.42%)

- Report follow-up time by treatment group.

Median Follow-Up Time (Days) [IQR]			
Patient Group	Optum	Truven	Medicare
Overall Patient Population	98 [38-209]	98 [44-236]	98 [38-206]
Referent	98 [38-190]	98 [44-192]	98 [38-188]
Exposure	98 [38-231]	119 [44-281]	98 [38-228]

- Report overall risk of the primary outcome.

	Optum	MarketScan	Medicare	Pooled
Risk per 1,000 patients	7.00	7.33	12.05	10.08

10. Final Power Assessment

Date conducted:

- Re-calculate power in the appropriate excel table, using the revised number of matched patients from the PS-match in Section 9. All other parameters in the table should be the same as in Section 8.

- For rivaroxaban vs. warfarin

- Pooled

Superiority Analysis		Non-inferiority Analysis	
Number of patients matched	102,636	Number of patients matched	102,636
Reference	51,318	Reference	51,318
Exposed	51,318	Exposed	51,318
Risk per 1,000 patients	10.08	Risk per 1,000 patients	10.08
Desired HR from RCT	0.79	Assumed HR from RCT	1
Alpha (2-sided)	0.05	Alpha (2-sided)	0.05
		Non-inferiority margin	1.46
Number of events expected	1034.57088	Number of events expected	1034.57088
Power	0.966450516	Power	0.999981559

o Optum

Superiority Analysis		Non-inferiority Analysis	
Number of patients matched	17,900	Number of patients matched	17,900
Reference	8,950	Reference	8,950

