3	Non-valvular Atrial fibrillation Subjects with newly diagnosed atrial fibrillation are eligible provided that: - there is evidence that the atrial fibrillation is non-valvular - cardioversion is not planned - there is ECG evidence on 2 occasions 24 hours apart demonstrating atrial fibrillation			
	For Inclusion Criteria 4 It is either A) History of ischemic stroke or TIA or arterial embolism -OR- B) 2 of the following 4 1) Heart failure 2) Hypertension 3) Age >=75 4) Diabetes			
4	History of prior ischemic stroke, TIA or non-CNS systemic embolism believed to be cardioembolic in origin	Measured any time prior to and including day of drug initiation in any diagnosis position and inpatient or outpatient care setting: Ischemic stroke: ICD-9 diagnosis: 433.x, 434. x, 436.xx TIA: ICD-9 diagnosis: 435.xx Systemic embolism: ICD-9 diagnosis: 444.xx	
Patorno, Elisabetta et al. "Cardiovascular outcomes associated with canagliflozin versus other non-gliflozin antidiabetic drugs: population based cohort study." BMJ 2018;360:k119 http://dx.doi.org/10.1136/bmj.k119
 
Patorno, Elisabetta et al. "Empagliflozin and the Risk of Heart Failure Hospitalization in Routine Clinical Care: A First Analysis from the Empagliflozin Comparative Effectiveness and Safety (EMPRISE) Study." Circulation. 2019 Apr 8. doi: 10.1161/CIRCULATIONAHA.118.039177
	
	OR 2 or more of the following risk factors	Measured anytime prior to and including day of drug initiation in any diagnosis position and inpatient or outpatient care setting:		
4a	– Heart failure and/or left ventricular ejection fraction ≤35%	Heart failure: ICD-9 diagnosis: 428.x, 398.91, 402.01, 402.11, 402.91, 404.01, 404.11, 404.91, 404.03, 404.13, 404.93	
Patorno, Elisabetta et al. "Cardiovascular outcomes associated with canagliflozin versus other non-gliflozin antidiabetic drugs: population based cohort study." BMJ 2018;360:k119 http://dx.doi.org/10.1136/bmj.k119
 
Patorno, Elisabetta et al. "Empagliflozin and the Risk of Heart Failure Hospitalization in Routine Clinical Care: A First Analysis from the Empagliflozin Comparative Effectiveness and Safety (EMPRISE) Study." Circulation. 2019 Apr 8. doi: 10.1161/CIRCULATIONAHA.118.039177
	

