5	
Female subjects must be postmenopausal (for at least 2 years), surgically sterile, abstinent, or, if sexually active, be practicing an effective method of birth control (e.g., prescription oral contraceptives, contraceptive injections, intrauterine device, double-barrier method, contraceptive patch, male partner sterilization) before entry and throughout the study; and, for those of childbearing potential, have a negative serum β-hCG pregnancy test at screening.
	N/A	We will incorporate this by excluding 'pregnant' women below.
6	Subjects must have signed an informed consent document indicating that they understand the purpose of and procedures required for the study and are willing to participate in the study	N/A	
7	In order to participate in the optional pharmacogenomic component, subjects must have signed the informed consent for DNA research document indicating willingness to participate in the pharmacogenomics component of the study (where local regulations permit)	N/A	
EXCLUSION CRITERIA			
1	Cardiac-Related Conditions		
1a	Hemodynamically significant mitral valve stenosis	
Measured 180 days prior to and including day of drug initiation in any diagnosis position and inpatient or outpatient care setting:
 
Mitral stenosis: ICD-9 diagnosis: 396.0x, 396.1x ICD-10 diagnosis: I34.2x, I05.1x, I05.2x
	
1b	Prosthetic heart valve (annuloplasty with or without prosthetic ring, commissurotomy and/or valvuloplasty are permitted)	
Measured 180 days prior to and including day of drug initiation in any diagnosis position and inpatient or outpatient care setting:
 
ICD-9 diagnosis: V43.3x ICD-10 diagnosis: Z95.2x
 
CPT procedure: (TAVR with prosthetic valve) 33361, 33362, 33363, 33364, 33365, 33366, 33367, 33368, 33369, 33477, 0483T, 0484T, 0569T, 0570T
	
1c	Planned cardioversion (electrical or pharmacological)	N/A	Will not capture 'planned' procedures
1d	Transient atrial fibrillation caused by a reversible disorder (e.g., thyrotoxicosis, PE, recent surgery, MI)	N/A	Transient AF would not be well captured in claims.

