Appendix B: Rivaroxaban vs Warfarin

COPD; n (%)	4,309 (16.8%)	2,430 (16.3%)	0.01	4,571 (14.2%)	2,352 (13.3%)	0.03	18,074 (19.6%)	8,952 (22.0%)	-0.06	26954 (17.9%)	13734 (18.7%)	-0.02
Asthma; n (%)	1,542 (6.0%)	1,081 (7.3%)	-0.05	1,625 (5.0%)	1,171 (6.6%)	-0.07	6,360 (6.9%)	3,495 (8.6%)	-0.06	9527 (6.3%)	5747 (7.8%)	-0.06
Obstructive sleep apnea; n (%)	2,457 (9.6%)	1,923 (12.9%)	-0.10	2,936 (9.1%)	2,260 (12.7%)	-0.12	7,564 (8.2%)	4,077 (10.0%)	-0.06	12957 (8.6%)	8260 (11.3%)	-0.09
Pneumonia; n (%)	1,531 (6.0%)	901 (6.1%)	0.00	1,914 (5.9%)	1,034 (5.8%)	0.00	8,764 (9.5%)	4,313 (10.6%)	-0.04	12209 (8.1%)	6248 (8.5%)	-0.01
Imaging; n (%)	36 (0.1%)	27 (0.2%)	-0.03	44 (0.1%)	15 (0.1%)	0.00	3,729 (4.0%)	1,328 (3.3%)	0.04	3809 (2.5%)	1370 (1.9%)	0.04
Other Medications												
Use of ACE inhibitors; n (%)	9,773 (38.0%)	5,230 (35.2%)	0.06	11,540 (35.7%)	6,215 (35.0%)	0.01	35,261 (38.2%)	15,477 (38.1%)	0.00	56574 (37.6%)	26922 (36.7%)	0.02
Use of ARBs; n (%)	5,359 (20.9%)	3,889 (26.2%)	-0.13	7,683 (23.8%)	4,892 (27.6%)	-0.09	20,854 (22.6%)	10,920 (26.9%)	-0.10	33896 (22.5%)	19701 (26.9%)	-0.10
Use of Loop Diuretics - United; n (%)	7,760 (30.2%)	3,674 (24.7%)	0.12	10,702 (33.1%)	3,963 (22.3%)	0.24	40,069 (43.4%)	15,255 (37.5%)	0.12	58531 (38.9%)	22892 (31.2%)	0.16
Use of other diuretics- United; n (%)	1,535 (6.0%)	731 (4.9%)	0.05	2,341 (7.2%)	878 (4.9%)	0.10	7,877 (8.5%)	2,806 (6.9%)	0.06	11753 (7.8%)	4415 (6.0%)	0.07
Use of nitrates-United; n (%)	2,055 (8.0%)	1,038 (7.0%)	0.04	3,094 (9.6%)	1,354 (7.6%)	0.07	10,921 (11.8%)	4,642 (11.4%)	0.01	16070 (10.7%)	7034 (9.6%)	0.04
Use of other hypertension drugs; n (%)	2,028 (7.9%)	1,125 (7.6%)	0.01	2,574 (8.0%)	1,303 (7.3%)	0.03	7,958 (8.6%)	3,455 (8.5%)	0.00	12560 (8.4%)	5883 (8.0%)	0.01
Use of digoxin- United; n (%)	4,005 (15.6%)	1,311 (8.8%)	0.21	6,378 (19.7%)	1,975 (11.1%)	0.24	17,796 (19.3%)	5,477 (13.5%)	0.16	28179 (18.7%)	8763 (12.0%)	0.19
Use of Anti-arrhythmics; n (%)	2,453 (9.5%)	2,071 (13.9%)	-0.14	3,881 (12.0%)	2,847 (16.0%)	-0.12	10,257 (11.1%)	6,110 (15.0%)	-0.12	16591 (11.0%)	11028 (15.1%)	-0.12
Use of COPD/asthma meds- United; n (%)	4,206 (16.4%)	2,858 (19.2%)	-0.07	5,916 (18.3%)	3,513 (19.8%)	-0.04	18,597 (20.1%)	9,406 (23.1%)	-0.07	28719 (19.1%)	15777 (21.5%)	-0.06
Use of statins; n (%)	15,187 (59.1%)	9,008 (60.6%)	-0.03	19,252 (59.6%)	10,616 (59.8%)	0.00	56,100 (60.7%)	25,111 (61.8%)	-0.02	90539 (60.2%)	44735 (61.1%)	-0.02

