Appendix B: Rivaroxaban vs Warfarin

Aspirin/dipyridamole; n (%)	73 (0.3%)	55 (0.4%)	-0.02	159 (0.5%)	118 (0.7%)	-0.03	374 (0.4%)	237 (0.6%)	-0.03	606 (0.4%)	410 (0.6%)	-0.03
Other antiplated agents; n (%)	151 (0.6%)	69 (0.5%)	0.01	182 (0.6%)	103 (0.6%)	0.00	601 (0.7%)	289 (0.7%)	0.00	934 (0.6%)	461 (0.6%)	0.00
PGP inhibitors; n (%)	10,770 (41.9%)	6,482 (43.6%)	-0.03	14,437 (44.7%)	8,199 (46.2%)	-0.03	44,650 (48.3%)	20,953 (51.5%)	-0.06	69857 (46.4%)	35634 (48.6%)	-0.04
Other gastroprotective agents; n (%)	182 (0.7%)	140 (0.9%)	-0.02	301 (0.9%)	204 (1.1%)	-0.02	1,082 (1.2%)	671 (1.7%)	-0.04	1565 (1.0%)	1015 (1.4%)	-0.04
Number of lipid tests ordered												
...mean (sd)	0.63 (0.82)	0.71 (0.84)	-0.10	0.27 (0.68)	0.40 (0.88)	-0.17	0.69 (0.83)	0.76 (0.89)	-0.08	0.59 (0.80)	0.66 (0.88)	0.00
...median [IQR]	0.00 [0.00, 1.00]	1.00 [0.00, 1.00]	-1.20	0.00 [0.00, 0.00]	0.00 [0.00, 1.00]	0.00	1.00 [0.00, 1.00]	1.00 [0.00, 1.00]	0.00	0.21 (0.91)	0.45 (1.01)	0.00
Proton pump inhibitor; n (%)	4,768 (18.6%)	3,236 (21.8%)	-0.08	6,352 (19.7%)	3,979 (22.4%)	-0.07	23,264 (25.2%)	11,663 (28.7%)	-0.08	34384 (22.9%)	18878 (25.8%)	-0.07
H2 receptor antagonist; n (%)	1,060 (4.1%)	632 (4.3%)	-0.01	1,125 (3.5%)	684 (3.9%)	-0.02	5,503 (6.0%)	2,836 (7.0%)	-0.04	7688 (5.1%)	4152 (5.7%)	-0.03
Vitamin K therapy; n (%)	20 (0.1%)	4 (0.0%)	0.04	57 (0.2%)	4 (0.0%)	0.06	119 (0.1%)	**	#VALUE!	196 (0.1%)	#VALUE!	#VALUE!
Number of neurologist visits												
...mean (sd)	0.29 (1.48)	0.36 (1.49)	-0.05	0.23 (1.34)	0.27 (1.34)	-0.03	0.49 (2.00)	0.54 (2.01)	-0.02	0.40 (1.79)	0.44 (1.77)	0.00
...median [IQR]	0.00 [0.00, 0.00]	0.00 [0.00, 0.00]	0.00	0.00 [0.00, 0.00]	0.00 [0.00, 0.00]	0.00	0.00 [0.00, 0.00]	0.00 [0.00, 0.00]	0.00	0.00 (1.98)	0.00 (1.92)	0.00
Number of INR (prothrombin) tests ordered												
...mean (sd)	2.68 (3.90)	0.29 (0.92)	0.84	1.90 (3.33)	0.23 (0.81)	0.69	3.68 (4.80)	0.39 (1.09)	0.95	3.13 (4.37)	0.33 (0.99)	0.01
...median [IQR]	1.00 [0.00, 5.00]	0.00 [0.00, 0.00]	0.35	0.00 [0.00, 2.00]	0.00 [0.00, 0.00]	0.00	1.00 [0.00, 6.00]	0.00 [0.00, 1.00]	0.29	0.39 (4.85)	0.00 (1.09)	0.00
Treating prescriber - Cardiologist; n (%)	12,149 (47.3%)	9,745 (65.5%)	-0.37	12,028 (37.2%)	10,681 (60.2%)	-0.47	46,370 (50.2%)	27,902 (68.6%)	-0.38	70547 (46.9%)	48328 (66.0%)	-0.39
Treating prescriber - Primary Care Physician; n (%)	16,835 (65.5%)	9,464 (63.6%)	0.04	9,639 (29.8%)	5,942 (33.5%)	-0.08	25,268 (27.3%)	12,084 (29.7%)	-0.05	51742 (34.4%)	27490 (37.5%)	-0.06

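### Neither the cohort criteria nor the propensity score has a cardioversion or AF ablation variable, so procedural rhythm control up to the index date is neither removed nor directly adjusted for

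*Combined protocol and SAP*

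**What the plan says.** The trial kept patients headed for cardioversion out in two places. Exclusion 1c reads "Planned cardioversion (electrical or pharmacological". Inclusion 3 admits newly diagnosed AF only if "cardioversion is not planned". In Appendix A the plan marks 1c N/A, with the rationale "Will not capture 'planned' procedures". The implementation cell for inclusion 3 is blank. The section 5.3 flowchart treats inclusions 2 and 3 as a single step, "Excluded based on Inclusion #2 & 3 - Atrial fibrillation", and has no cardioversion or ablation step anywhere.

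For adjustment, section 6.2 says the covariates beyond age, sex and comorbidity index "are listed in Table 1 (Appendix B", and section 9 says: "The PS should include the complete list of covariates (excluding laboratory values, which are missing in some patients". Neither the unmatched nor the matched Table 1 has a cardioversion or ablation row. The cardiac procedure rows are coronary revascularisation (CABG, PTCA, stent) and tests such as ECG, echocardiogram and stress test.

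Table 1 does carry rhythm-related rows, including "Use of Anti-arrhythmics; n", "Treating prescriber - Cardiologist; n", other cardiac dysrhythmia and digoxin. Exclusion 3f, for an unrelated reason (CYP inhibition), also removes patients with amiodarone dispensed in the 4 days up to and including the index date.

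**The concern.** The reason given for N/A covers intention only. Claims cannot show that a cardioversion is planned, but a cardioversion or ablation already performed leaves a procedure code. The plan uses such codes elsewhere: 1b identifies prosthetic valves partly by CPT code, and 2b excludes major surgery by procedure code in the 30 days up to and including initiation. Nothing explains why the same was not done here, if only as a covariate.

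A patient who starts an anticoagulant around a cardioversion or ablation and takes no antiarrhythmic drug is identified only through general markers of cardiology care. If such patients have a different stroke risk and are unevenly split between the matched arms, the hazard ratio carries confounding that more data will not reduce.

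**Working it through.** **1. What the PS already covers.** All counts are from Table 1, Appendix B, pooled unless stated. The standardized difference (SMD) is (p_w − p_r) / √{[p_w(1−p_w) + p_r(1−p_r)]/2}, with w = warfarin and r = rivaroxaban.

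Antiarrhythmics before matching: 16,591/150,399 = 0.1103 and 11,028/73,269 = 0.1505, so SMD = −0.0402/0.3362 = −0.120 (stated −0.12). After matching: 6,557/51,318 = 0.1278 and 6,642/51,318 = 0.1294, so SMD = −0.005 (stated 0.00). The plan's figures reproduce.

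| Matched covariate | Warfarin | Rivaroxaban | SMD |
|---|---|---|---|
| Antiarrhythmics, pooled | 12.8% | 12.9% | 0.00 |
| Cardiologist prescriber, pooled | 63.7% | 62.6% | 0.02 |
| Other cardiac dysrhythmia, pooled | 55.9% | 55.4% | 0.01 |
| Any ECG, pooled | 80.2% | 82.6% | −0.06 |
| Any ECG, MarketScan | 71.5% | 76.2% | −0.11 |
| Echocardiogram, pooled | 53.6% | 56.7% | −0.06 |
| Echocardiogram, MarketScan | 46.2% | 51.5% | −0.11 |
| Digoxin, pooled | 15.4% | 12.8% | 0.07 |
| Digoxin, MarketScan | 17.1% | 12.5% | 0.13 |

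The drug-based marker and the prescriber marker balance. Some general work-up markers and digoxin do not, chiefly in MarketScan. These markers are indirect: they do not show a cardioversion imbalance, but they show that balance on antiarrhythmics does not ensure balance on AF management as a whole.

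**2. Possible size.** The documents give neither the frequency of baseline cardioversion or ablation nor its relation to stroke, so every input here is an assumption. If shares p₁ (rivaroxaban) and p₀ (warfarin) of the matched arms are affected, with stroke rate ratio RR against other patients, the hazard ratio is multiplied by [1 + p₁(RR−1)] / [1 + p₀(RR−1)].

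| p₁ v p₀ | RR 0.5 | RR 2.0 |
|---|---|---|
| 5% v 3% | 0.990 | 1.019 |
| 10% v 5% | 0.974 | 1.048 |
| 15% v 10% | 0.974 | 1.045 |

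Two further cases: 5% v 4% with RR 0.7 gives 0.985/0.988 = 0.997, and 10% v 5% with RR 0.4 gives 0.940/0.970 = 0.969.

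**3. Against the plan's precision.** Section 10 expects 1,034.6 pooled events, so SE(log HR) ≈ 2/√1034.6 = 0.062. The outer factors are ln(0.969) = −0.031 and ln(1.048) = 0.047, or about 0.5 and 0.75 of a standard error. Applied to the trial's hazard ratio of 0.79, they give 0.79 × 0.969 = 0.77 and 0.79 × 1.048 = 0.83.

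**The case against.** The plan is open that 1c cannot be emulated, and its reason is accurate. Criterion 1c concerns a future cardioversion: a patient anticoagulated ahead of one has no procedure code at baseline, and using codes after the index date would condition on the future. Ablation is not named in 1c at all. Baseline codes therefore do not restore the trial's criterion. All of that stands, and it limits what the fix can be called.

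A reader might infer from the pre-matching figures (antiarrhythmics 11.0% v 15.1%; cardiologist prescriber 46.9% v 66.0%) that rhythm-control patients in general are unadjusted. The documents do not support this. Both variables are in Table 1, both balance after matching, and recent amiodarone dispensing is an exclusion.

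A reader might also infer that patients on a short intended course went to rivaroxaban, so that the bias favours rivaroxaban. The section 9 tables give no sign of it. End of index exposure accounts for 70.19% of warfarin and 70.07% of rivaroxaban patients. Median follow-up is 98 days in both arms in Optum and Medicare, and longer for rivaroxaban in Truven (119 v 98 days). Nor do the documents say whether these patients have lower or higher stroke risk.

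Finally, the assumed imbalances are generous. The antiarrhythmic ratio was 15.1/11.0 = 1.37 before matching and about 1.01 after it, while 10% v 5% is a twofold difference after matching. The any-ECG imbalance is also softened by equal mean ECG counts (2.40 v 2.39).

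The objection does not answer why procedures already performed, which the data can show, are left out of the PS when the plan uses procedure codes for other criteria.

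**Conclusion.** The point holds in a narrow form. Planned cardioversion is a disclosed gap and not a contradiction. Separately, procedural rhythm control performed on or before the index date is neither removed nor directly adjusted for, while drug-based rhythm control is adjusted for and balanced.

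The direction and size of any bias are unknown. The factor of about 0.97 to 1.05 rests wholly on the assumed frequencies and rate ratios above, spans 1, and amounts to at most about three-quarters of a standard error. It supports no claim that the result would be tilted towards rivaroxaban or towards the trial's finding. This is a cheap improvement to confounding control, not a flaw that threatens the study.

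Two further dependencies: the content of the PS is inferred from section 9 and Table 1, since no fitted model is shown; and Appendix A refers to an external folder for further detail, which was not available.

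**What to change.** Add two baseline covariates to Table 1 and the PS: electrical cardioversion and AF ablation, each in the 180 days up to and including the index date. Re-match before any comparative analysis and report both rows before and after matching, by database and pooled. If the procedures prove rare or balanced, those rows settle the matter.

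Optionally, run one sensitivity analysis that excludes patients with a cardioversion in the 30 days up to and including the index date, the window that 2b already uses for major surgery. Label it as a check on peri-cardioversion starters and not as an emulation of 1c. Do not use post-index procedures for exclusion or adjustment.

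The cost is a little programming on data already held, one re-match and possibly a few matched pairs. The section 9 and 10 tables would need refreshing and the review step in section 10 repeating. Pooled power (0.966 for superiority, 0.99998 for non-inferiority) leaves room for losing a few pairs. The dates in section 13 are blank, so on this document the change can still be pre-specified.
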